13.21 Primary Outcome Variable

The primary outcome variable will be the combined AUC for the “fatigue at its worst” item of the BFI. The value of this variable for patient i is denoted $bfi(i)$ and is comprised of the BFI scores collected during the 8 weeks of the study period.

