5.0 Study Design

Using a Phase II blinded, randomized placebo-controlled trial, with optional open label extension period, we will evaluate armodafinil's ability to reduce patient-reported fatigue in patients with treated head and neck cancer. This type of trial design is especially important in trials where symptom reduction is the outcome and where knowledge of the treatment arm might bias assessment by the staff or patient. We will purchase commercial grade drug and matching placebo to be dispensed by the investigational pharmacy.

Design: Phase II blinded, randomized placebo-controlled trial, with optional open label extension period

Symptom Intervention Agent: Armodafinil

Study Period: 8-12 weeks depending on participation in the optional open label component : intervention agent daily for 4 weeks (Part I), with continued assessment follow-up period of 4 weeks (Part II). At the end of the 4-week agent intervention, the patient will be given the option to receive open label armodafinil during the 4 weeks follow-up period. If the patient agrees to this option, the follow-up period for these patients will be extended for another 4 weeks.

Primary Symptom Outcome Variable: 4-week (+/- 7 days) area under the curve (AUC) for patient-reported fatigue at its worst (item from the Brief Fatigue Inventory).

Secondary outcomes assessed will include: (1) the 5 most-severe MDASI-HN symptoms at 2-month follow up based on previously collected MDASI-HN data (2) overall MDASI-HN symptom severity, (3) overall MDASI-HN interference, (4) patient-reported alertness (via Epworth Sleepiness Scale), and (5) work productivity and activity impairment questionnaire.

Forty patients will be randomized to either armodafinil or placebo, twenty in each arm. AUC values for patients who drop out of the study after providing 2 weeks of AUC data will be included by carrying their last symptom data forward for the remaining study period under the intent-to-treat rule. The carry-forward method of handling drop-outs will be revisited upon completion of the study to determine if adjustments to these values can be made using longitudinal regression models estimated from patients who completed the entire study.

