6.0 Administration of Pharmacologic Agent

Armodafinil or placebo will begin after enrollment and will continue daily for a total of 4 weeks.

Patients will pick up the assigned study medication at one of the outpatient pharmacy stations in MD Anderson. At pickup, patients will receive instruction on how to take study medications (Appendix EEE). If the patient is unable to pick up the study medication, the investigational pharmacy will mail the study medication to the patient home, overnight.

The participants will take study medication enterally, once daily, in the morning, starting after study entry and continuing for 28 days (4 weeks). The dosing schedule for the symptom intervention agent is described in the table below.

Study medication use will be reviewed at the end of week 4 by study staff. Patients will be asked to bring their study medication to the clinic if they are coming in for a routine visit, at which time study staff will perform a medication count. If the patient is not coming to the clinic at study completion, the medication review will be completed by telephone. Results of the count will be recorded on the Study Medication Accountability form (Appendix K).

During the end of week 4 assessment, the study staff will also offer the participant the option to receive open label armodafinil, at the same dosing schedule described in the table below. If the patient agrees to the optional open label extension, they will either pick-up armodafinil during their routinely scheduled follow-up visit or the pharmacy will mail it to them. A 5-day window will be allowed between the end of Part I and the start of the optional open label extension.

Symptom Intervention Agent	Dosage Forms	Total daily dose: starting day 1 of week 1
Armodafinil or matching placebo	50mg and 100mg capsules or tablets	50 mg the first 3 days, 100 mg the next 4 days, and 150 mg for the remaining treatment period.*

*capsules or tablets, one every morning, may be given without regard to meals. This dosing schedule is to be followed during the 4-week symptom intervention and the optional open label extension.

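### The primary AUC window is contradictory: 4 weeks (± 7 days) in Section 5.0, but 8 weeks, including off-drug or open-label time, in Section 13.21

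*Combined protocol and SAP*

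**What the plan says.** All references are to the combined protocol and SAP.

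- **Section 5.0 (Study Design)** labels the endpoint: "Primary Symptom Outcome Variable: 4-week (+/- 7 days) area under the curve (AUC) for patient-reported fatigue at its worst".
- **Section 13.21 (Primary Outcome Variable)**, inside the statistical analysis plan, calls the variable a 'combined' AUC of the same BFI item, a term it does not define, and says that it "is comprised of the BFI scores collected during the 8 weeks of the study period".
- **Section 5.0** describes the course of the study as "intervention agent daily for 4 weeks (Part I), with continued assessment follow-up period of 4 weeks (Part II"; in Part II "the patient will be given the option to receive open label armodafinil during the 4 weeks follow-up period". The overall duration is given as "Study Period: 8-12 weeks depending on participation in the optional open label component".
- **Section 6.0** limits the randomised agent to 28 days. It does not restrict the open-label offer to one arm.
- **Section 5.0** handles patients who leave after at least 2 weeks of data by "carrying their last symptom data forward for the remaining study period under the intent-to-treat rule", and says that this method will be looked at again when the study is complete.
- **Section 13.1** gives the power: 20 per arm, 0.70 SD on the BFI AUC, 70% power, one-sided 5%, with 0.70 SD equated to about 1.7 points on a 0 to 10 scale. No window is named.
- **Section 13.2** regresses the AUC on indicators of the treatment a patient received, whereas Sections 5.0 and 13.23 invoke intention to treat.

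**The concern.** Two sections of current text define the same primary variable over different periods. An analyst following Section 5.0 and one following Section 13.21 would run different primary tests on the same trial, and the plan has no rule for choosing between them. If the choice is left open until after unblinding, it can be made with the results in view.

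The difference is one of substance. Over weeks 1-4 the AUC compares blinded armodafinil with blinded placebo. Over weeks 1-8 it mixes that comparison with a period in which nobody is on randomised agent and some patients, by their own choice, take open-label armodafinil, for a patient-reported score. Section 5.0 itself argues that blinding matters for this kind of outcome.

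Sections 13.1 and 13.2 say that the trial is meant to supply effect-size and variability estimates for a larger study. The designers of that study would need to know which period the estimate describes.

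**Working it through.** **1. Can the two definitions be read as one?** Section 5.0 allows 4 weeks ± 7 days, that is 3 to 5 weeks. Section 13.21 uses 8. The ranges do not meet. If 'combined' means Part I plus Part II, that explains the 8 weeks but still contradicts Section 5.0. Appendix X (the assessment schedule) is not in the available text. A schedule would show when BFI is collected; it would not by itself choose between two explicit definitions.

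**2. What each window contains** (Sections 5.0 and 6.0).
- Weeks 1-4: randomised, blinded armodafinil or placebo in every patient.
- Weeks 5-8: no study drug, or open-label armodafinil, in either arm. A former placebo patient may be on active drug while a former armodafinil patient is off it.

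Over 8 weeks the wording in Section 13.2 about treatment received also becomes ambiguous, because a placebo patient who opts for open label has received both.

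**3. Reproducing the stated power** (inputs from Section 13.1: 20 per arm, d = 0.70, one-sided 5%).
- Noncentrality = 0.70 × √(20/2) = 2.21, with 38 degrees of freedom.
- Noncentral t power = 70.2%; normal approximation = 71.5%.
- Implied SD = 1.7 / 0.70 = 2.43 points.

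The 70% reproduces. The calculation uses a standardised effect with no period attached, so it cannot reveal which window was meant.

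**4. Carry-forward.** For a patient who leaves just after week 2, which is the extreme case, the last value fills 2/4 = 50% of a 4-week AUC but 6/8 = 75% of an 8-week AUC. The documents give no dropout rate, so the number of patients affected is unknown.

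**5. Scale.** If the AUC is a raw area, constant fatigue yields an area 35/21 = 1.67 times as large over 35 days as over 21, the extremes of ± 7 days. A time-average removes that. Section 13.1 quotes its effect on a 0 to 10 scale, which suggests a time-average but does not state one.

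**6. Illustration only: how the windows could differ.** Assumptions not in the documents: 0.70 SD belongs to weeks 1-4; the AUC is time-averaged; SDs are equal in the two periods; the two 4-week means correlate at r = 1.0 to 0.3; and the arm difference in weeks 5-8 is a fraction f of that in weeks 1-4. Then the 8-week effect size is 0.70 × (1 + f)/2 ÷ √((1 + r)/2).

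| f | Difference (points) | 8-week effect size | Power |
|---|---|---|---|
| 1 | 1.70 | 0.700-0.868 | 70-85% |
| 0.5 | 1.28 | 0.525-0.651 | 49-65% |
| 0 | 0.85 | 0.350-0.434 | 29-38% |
| -0.5 (reversed) | 0.43 | 0.175-0.217 | about 13-17% |

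The differences are 1.7 × (1 + f)/2; the last effect sizes are 0.70 × 0.25 = 0.175 and 0.175/√0.65 = 0.217. The results run from far below 70% to above it, depending on inputs that the plan does not supply.

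**The case against.** **The documents do not prove that 4 weeks was intended.** This stands. Section 13.21 is the statistical section, and 'combined' may have been a deliberate reference to both parts. The recommendation for 4 weeks rests on its match with the blinded period and with the labelled outcome in Section 5.0. What is not optional is that the sponsor state one window.

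**A reader might infer that the trial is underpowered, or that an 8-week AUC must lose power.** The documents do not support this. They give neither persistence of effect nor open-label uptake; if 0.70 SD was set for 8 weeks, power over 8 weeks is 70%; and under full persistence it could be higher.

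**A reader might infer that week-4 scores will be contaminated by open-label drug, and that late ones should be set aside.** Section 6.0 says "A 5-day window will be allowed between the end of Part I and the start of the optional open label extension", which lies inside the + 7 days. But it also says "During the end of week 4 assessment, the study staff will also offer the participant the option to receive open label armodafinil", so the score should normally precede any open-label dose. Without Appendix X an overlap cannot be shown. Discarding an observed in-window score because of a choice made after randomisation would bring a problem of its own.

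**The side issues are smaller than the main one.** This is fair. The 8 weeks in Section 13.21 can be read as the 8 weeks common to all patients, so the 8-12 week study period adds little. The wording about treatment received matters much less once the window is 4 weeks. The carry-forward method is already due to be revisited. None of this removes the contradiction.

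**Conclusion.** The contradiction is real, and it rests on the text alone: 3 to 5 weeks in one section, 8 in the other, for the one variable that must be unambiguous before unblinding. Followed as written, Section 13.21 gives a primary comparison that does not isolate blinded armodafinil from placebo. The effect size in Section 13.1 is not tied to either window.

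Confidence is high on those points. It does not extend to the size or direction of the difference between the two analyses, which cannot be derived from the documents. The power table is an illustration under stated assumptions and carries no weight in judging how serious the point is. The plan's 70% figure is arithmetically sound.

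**What to change.** Before unblinding:

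1. **Section 13.21.** Reconcile it with Section 5.0: define the primary AUC on BFI worst-fatigue scores through the end of week 4 (Part I). Delete or define 'combined'. Express the AUC as a time-average, so that the ± 7 days does not change its scale. End carry-forward for this AUC at week 4.
2. **Section 13.2.** Regress on randomised arm instead of treatment received. Report any 8-week AUC as secondary, with open-label uptake described by arm.
3. **Section 13.1.** Name the window to which 0.70 SD and 1.7 points apply. If they were not derived for 4 weeks, restate them.

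**Cost.** Items 1 and 2 are wording and need no new visits. Item 3 may need more than wording, because the sponsor has to trace where the effect size came from. The real downside is that weeks 5-8 leave the primary test. If the effect persisted in full, this could forgo some power: up to about 15 points (85% against 70%) under the illustrative equal-SD assumptions above.

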13.22 Secondary Outcome

We will use linear mixed models determine whether the placebo and the armodafinil groups differ on our secondary outcomes: the 5 most-severe symptoms, symptom interference, work productivity, and sleepiness.

We are also interested in exploring predictors of survival. Univariate Cox proportional hazards models will be used to screen for potential predictors (symptoms, demographic and clinical variables) of overall survival. Standard model fitting diagnostics will be performed. Finally, Kaplan-Meier survival curves will be plotted.

13.23 Non-Compliance with Study Agent

Patients who do not comply with study agent dosing requirements will remain in the study under the intent-to-treat rule.

